6.3 Removal of Patients from Therapy or Assessment

6.3.1 Discontinuation of Individual Patients

A patient may withdraw from the study at any time at his/her own request for any reason without prejudice to future medical care by the physician or at the institution. A patient may be withdrawn at any time due to the following reasons:

1. At the discretion of the Investigator or the Sponsor for safety, behavioral, compliance, or administrative reasons;
2. At the discretion of the Sponsor/Medical Monitor, if a patient receives a prohibited concomitant medication according to [Table 1 \(Section 6.4.7.2\)](#).

In addition, any patient who becomes pregnant during the Treatment Period or within 7 days after the last dose of study drug should be withdrawn from the study ([Section 6.5.2.6](#)).

Whenever possible, withdrawal of a patient from study drug by the Investigator should be discussed with the Medical Monitor before the patient stops study drug.

If study drug is discontinued, regardless of the reason, an Early Termination Visit should be completed after the last dose of study drug or, as soon as feasible. The Follow-up Visit is to be completed 7 to 10 days after the Early Termination Visit.

If study drug is discontinued, although a patient will not be obliged to give a reason for withdrawing prematurely, the Investigator must make a reasonable effort to obtain the reason while fully respecting the patient's rights. The reason(s) for termination and date of stopping study drug must be recorded on the electronic case report form (eCRF) and source documents.

If a patient discontinues early due to an adverse event, the event will be followed until resolution, the patient returns to baseline status, the condition stabilizes, or the patient is lost to follow-up.

If the patient withdraws consent for disclosure of future information, the Sponsor may retain and continue to use any data collected before such a withdrawal of consent.

Patients who discontinue after the administration of the first dose of study drug will not be replaced.

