8 STATISTICAL METHODS

8.1 General statistical conventions

All statistical procedures will be completed using SAS version 9.2 or higher.

Unless otherwise noted, continuous variables will be summarized using descriptive statistics, including number of patients with non-missing observation (n), mean, median, standard deviation (SD), minimum (min) and maximum (max). Means and medians will be reported to one decimal place more than the raw data. Standard deviation will be reported to two more decimal places than the raw value. The minimum and maximum will be reported to the same decimal as the raw data.

Categorical variables will be summarized using the frequency count and the percentage of patients in each category. All percentages will be rounded to one decimal point. The number and percentage of patients will always be presented in the form XX (XX.X%) where the percentage is in parentheses. To ensure completeness, all summaries for categorical and discrete variables will include all categories, even if none of the patients in a particular category. Counts of zero in any category will be presented as “0”. Unless otherwise noted, for all percentages, the number of patients in the analysis population for the treatment group will be the denominator.

“Baseline” will be defined as per [section 7.1](#). For efficacy endpoints, “on-treatment” is defined as any assessment following the first dose of study drug and within 2 days from the last dose of study drug recorded in the patient diary. For safety endpoints (excluding adverse events), any assessment within 7 days after last dose of study drug will be deemed “on-treatment”. For all endpoints “End of treatment” (EOT), in summaries, will be represented by the last non-missing on-treatment value recorded up to and including the Week 12/Early Termination visit. Treatment emergence for adverse events is described in [section 8.7.1](#). Summaries will be presented across all scheduled visits and EOT unless stated otherwise. Only on-treatment data will be used in summaries and statistical analyses (with the exception of the Patient Global Impression of Change).

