8.7.1 Adverse events

All adverse events (AE) will be coded using MedDRA dictionary to the corresponding MedDRA system organ class (SOC) and Preferred Term (PT) for standardization and summary purposes. Only treatment emergent adverse events (TEAEs) will be included in summary tables, except for a table presenting an overall summary of all AES and of REAEs. Summaries will provide results overall and by treatment.

TEAEs are defined as adverse events (AEs) with an onset date on or after the first dose of the study drug up to the End of Treatment/Early Termination visit or 7 days after the last dose, whichever is later.

The incidence of TEAEs will be presented using counts and percentages of patients with adverse events and tabulated by SOC and preferred term. System organ class will be sorted alphabetically and preferred term within SOC will be sorted by descending frequency based on the incidence across all patients in the safety population. A patient will be counted only once in the incidence count for a MedDRA SOC or preferred term, although a patient may have multiple occurrences (start and stop) of an event associated with a specific MedDRA preferred term or SOC.

The following specific summary tables will be generated:

- An overall summary showing the number and percentage of patients with
 - Any AE (both TEAE and non-TEAE)
 - TEAE
 - Serious TEAE
 - Serious non-TEAE
 - Related TEAE
 - Severe TEAE
 - TEAE leading to drug interruption
 - TEAE leading to dose reduction
 - TEAE leading to study drug discontinuation
 - Number of any events and number of TEAEs (Count only)
- TEAEs by SOC and preferred term
- TEAEs related to study drug by SOC and preferred term
- TEAEs by SOC, preferred term and maximum severity
- TEAEs occurring in $\geq 5\%$ of patients in at least 1 treatment group
- Treatment-related TEAEs occurring in $\geq 5\%$ of patients in at least 1 treatment group

Statistical Analysis Plan (SAP)

- Serious TEAEs by SOC and preferred term
- TEAEs leading to study drug discontinuation by SOC and preferred term

If the relationship to the study drug of an adverse event (AE) is missing, the AE will be categorized as “related” to the study drug. If a patient reports 2 or more AEs that code to the same preferred term, the event with the maximum relationship will be included in the table.

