8.7.2 Clinical laboratory evaluations

Blood samples for clinical laboratory tests, including hematology, serum chemistry and serum pregnancy will be collected during screening and day 1 before study drug administration, on week 6 and week 12 (end of treatment).

All clinical laboratory data will be reported in Système International units.

Summary statistics for each scheduled time point measured and mean changes from baseline to each time point will be presented for hematology and serum chemistry laboratory results. The baseline value is defined as the last observation prior to or on the date of the first dose of study drug whether scheduled or unscheduled (see [section 7.1](#)).

Hematology and serum chemistry laboratory test results will be assigned as Low (L), Normal (N) or High (H) classification according to whether the value was below (L), within (N), or above (H) the laboratory parameter’s reference range.

Statistical Analysis Plan (SAP)

Comparisons will be based on 3×3 tables (shift tables) that, for a particular laboratory test, compare the baseline L/N/H classification to the highest and/or lowest L/N/H classification during the treatment period.

Clinically important laboratory values based on the below specified criteria will also be summarized.

- Alanine aminotransferase (ALT), aspartate aminotransferase (AST),
 - $>3 \times$ ULN
 - $>5 \times$ ULN
 - ALT $>3\times$ ULN or AST $>3\times$ ULN
- Alkaline phosphatase (ALP)
 - $>1.5 \times$ ULN
- Total Bilirubin (TBILI)
 - $>2 \times$ ULN
- AST and Total Bilirubin
 - AST $>3\times$ ULN and TBILI $>2\times$ ULN
- ALT and Total Bilirubin
 - ALT $>3\times$ ULN and TBILI $>2\times$ ULN
- AST or ALT and Total Bilirubin
 - AST or ALT $>3\times$ ULN and TBILI $>2\times$ ULN

A summary of treatment emergent sodium findings will also be provided, categorizing results into those <146 mmol/L, $146 - 150$ mmol/L, and >150 mmol/L at the 6 and 12 week assessments. An additional summary will present these categories for subjects over the full study period presenting the highest category attained (at any on-treatment assessment) and sustained (at any on-treatment assessment and all subsequent on-treatment assessments); this analysis will include both scheduled and unscheduled laboratory test results.

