8.7.4 Electrocardiograms

ECG assessment will be done at screening, day 1 and end of treatment (EOT).

ECG results include an overall interpretation of 'normal,' 'abnormal but not clinically significant,' or 'abnormal and clinically significant.' These results will be tabulated at each time point using a shift table.

Electrocardiogram results will be listed for all available visits, including visit, whether ECG was performed (yes/no), explanation (if not performed), assessment date/time, overall interpretation.

Statistical Analysis Plan (SAP)

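### The SAP's 7-day cut-off for laboratory, vital-sign and ECG data is shorter than its TEAE window, so a late Early Termination visit can leave an early stopper with no post-baseline ECG, and sometimes no sodium or liver result, in the safety tables

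*SAP*

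**What the plan says.** SAP 8.1 defines the window for safety data other than adverse events: "For safety endpoints (excluding adverse events), any assessment within 7 days after last dose of study drug will be deemed" on-treatment. The same paragraph adds the exclusion, "Only on-treatment data will be used in summaries and statistical analyses", and excepts only the Patient Global Impression of Change. It also defines the EOT value as "represented by the last non-missing on-treatment value recorded up to and including the Week 12/Early Termination visit", so a late ET result cannot enter as the EOT value.

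SAP 8.7.1 counts TEAEs "up to the End of Treatment/Early Termination visit or 7 days after the last dose, whichever is later".

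Protocol 6.3.1 says that after discontinuation "an Early Termination Visit should be completed after the last dose of study drug or, as soon as feasible". It gives no upper limit.

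Post-dose safety measurements are few. SAP 8.7.2 schedules blood samples at screening and "day 1 before study drug administration, on week 6 and week 12 (end of treatment"). SAP 8.7.4 says "ECG assessment will be done at screening, day 1 and end of treatment (EOT"), which leaves one scheduled post-dose ECG. The Schedule of Events makes the Follow-up Visit a phone contact unless otherwise necessary, so the ET visit is normally the last chance to draw blood or record an ECG.

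**The concern.** The two safety windows in the SAP differ, and no reason is given. The difference affects only patients who stop early and are seen late. For them, an event found at the ET visit is tabulated as a TEAE, while the blood result or ECG from the same visit is left out of the laboratory or ECG table.

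Sodium and liver values matter here. Protocol 4.3 names hypernatremia and dehydration as effects of the drug in people with normal renal function, and says only that they are expected to be largely reduced in stage III to IV patients not on dialysis. The interim safety package in SAP 8.9.2.5 includes summaries of clinically important laboratory values and sodium, and doses found unsafe or poorly tolerated are dropped at that point. The SAP covers both interim and final analyses and states no separate interim window.

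The denominator is also unsettled. SAP 8.1 makes the analysis population the default, so an excluded patient could be counted as having no abnormality. Protocol 8.7.3 restricts laboratory summaries to patients with a post-baseline time point, so the same patient would drop out. Under neither rule does the table show the result that was measured.

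**Working it through.** There is no planned figure to reproduce, because the point is a data-inclusion rule. I applied the rule to the visit schedule.

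**Inputs**
- A value is on-treatment if assessment day ≤ last-dose day + 7 (SAP 8.1).
- Post-dose laboratory draws: Week 6 (Day 42) and Week 12/ET (SAP 8.7.2).
- Post-dose ECG: EOT/ET only (SAP 8.7.4).
- Vital signs: Days 14, 28, 42, 56, 70 and EOT/ET (Schedule of Events).
- Assumptions: no unscheduled on-treatment test, and no clinic visit between the last dose and the ET visit.

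**Result for each early last-dose day, 1 to 83**

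| ET visit after last dose | ECG | Sodium and liver | Vital signs |
|---|---|---|---|
| 7 days or less | kept | kept | kept |
| 8 days or more | none in tables, last-dose days 1-83 | none, last-dose days 1-41 | none, last-dose days 1-13 |

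A patient who stops on or after Day 42 keeps the Week 6 laboratory value and loses only the later one. For example, a last dose on Day 18 with the ET visit on Day 28 gives a gap of 28 − 18 = 10 days. The ECG and blood results from that visit are excluded, and no earlier post-dose ECG or blood draw was scheduled.

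The laboratory range depends on two readings:
- The column for the mid-study draw in the SAP schedule table is hard to read in the text available. If it is Week 4 (Day 28), the affected last-dose days are 1-27.
- If a patient who had stopped still attended on Day 42 before a later ET visit, that draw would count for last-dose days from 42 − 7 = 35 onward, leaving 1-34.

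**Scale.** The documents give neither a discontinuation rate nor a distribution of delay to the ET visit. Assume 10-20% stop early, 10-50% of those have a late ET visit, and stopping days are uniform over Days 1-83.
- ECG lost, 60 per arm: 60 × 0.10 × 0.10 = 0.6 to 60 × 0.20 × 0.50 = 6 patients.
- All laboratory results lost: multiply by 41/83, giving 0.3 to 3.0 patients.
- With 120 per arm: 1.2 to 12 and 0.6 to 5.9 patients.

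**Effect of widening the window, by table**
- *Highest sodium category, liver thresholds, worst-value shifts, notable vital signs:* an extra value can only leave the patient's worst category unchanged or move it further out.
- *EOT value:* this is the last qualifying value, so an off-drug ET result would displace an on-drug one.
- *Sustained sodium:* SAP 8.7.2 defines it as "sustained (at any on-treatment assessment and all subsequent on-treatment assessments"). Take a patient above 150 mmol/L at Week 6 and below 146 mmol/L at a late, off-drug ET visit. Under the present rule the elevation is sustained. With the wider window it would no longer be.

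**The case against.** The strongest reply is that the documents already catch what matters:
- SAP 8.7.2 plans a separate listing that flags raised liver tests and sodium of 146 mmol/L or more, and shows all of a flagged patient's data for that parameter across the study. It states no on-treatment limit.
- ECGs are listed for all available visits.
- New clinically significant laboratory abnormalities are adverse events (Protocol 6.5.2.1.1), and clinically significant ECG findings after the first dose are TEAEs (Protocol 6.5.2.4). The TEAE window reaches the ET visit.
- The interim package includes adverse event tables and listings, so dose decisions do not rest on laboratory tables alone.

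This stands and limits the consequence. It does not remove it: listings do not compare arms, and a value can cross a threshold without being reported as an adverse event.

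Separating on-drug from off-drug values is also defensible. For laboratory shift tables, Protocol 8.7.3 refers to the treatment period, which Protocol 8.7.1 ends at the last dose, so the SAP is wider there. For vital signs, however, Protocol 8.7.4 plans summaries of each post-baseline assessment, and SAP section 9 does not list the 7-day limit as a change.

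A reader might infer that about half of early stoppers lose these data. That follows only if the ET visit waits for the next 14-day visit: stopping s days after a visit leaves a gap of 14 − s, which exceeds 7 for s = 0 to 6, or 7/14. The protocol instead asks for the visit as soon as feasible, so 50% is a scenario and not an estimate.

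**Conclusion.** The mismatch is real and follows from the text. With an ET visit 8 or more days after the last dose and no unscheduled test, every early stopper is missing from the post-baseline ECG tables, and those who stopped before the mid-study draw are also missing from the sodium and liver tables. Complete loss of vital signs is confined to stopping before Day 14.

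The size cannot be derived from the documents and is probably small. The figures of 0.6-6 patients per arm of 60 (ECG) and 0.3-3 (all laboratory results) rest wholly on the assumed rates. Even so, rare liver or sodium events come in counts of the same order.

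Two stronger readings are not supported. One is that the rule understates risk in the less-tolerated arm. This is possible, because the missing values belong to patients who stopped, but nothing in the documents shows that stopping or delay will differ by arm. The other is that the TEAE window should replace the 7-day window in every table. That could mask an on-drug abnormality in the EOT value and in the sustained sodium category.

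**What to change.** Amend SAP 8.1 and the table specifications, for both interim and final analyses:
- Keep the 7-day on-treatment definition for the EOT value, the by-visit change-from-baseline summaries and the sustained sodium category.
- For the liver-threshold, highest-sodium-category-attained, worst-value shift, notable vital-sign and ECG tables, include all post-baseline values up to the later of the EOT/ET visit or 7 days after the last dose. Alternatively, add an any-post-baseline version beside the on-treatment one. That is the cleaner choice for ECG if a patient also has an unscheduled on-treatment tracing.
- State the denominator for these tables.
- Show days since last dose in the listings, and record the window in SAP section 9.

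This needs a few sentences and some table reprogramming. It needs no new data, leaves the timing of the ET visit as it is, and does not touch the efficacy analyses. The cost is that some added values will come from patients more than a week off drug, which the days-since-last-dose column makes visible.

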8.2 Subject disposition

The number of enrolments, screen failures, randomizations and treated patients will be summarized over all patients. In addition, the number of each reason for screen failure will be provided. In this summary table, percentages will be calculated using the number of enrolments as the denominator.

The number and percent of screen failure patients failing each inclusion and exclusion criteria at least one once will be summarized. The percentages will be calculated using the number of patients in the enrolled population.

A separate display will present the number and percent of patients who receive study treatment, complete the 12-week study treatment, who discontinue from double-blind treatment, (and the reason for study treatment discontinuation), and who complete the follow-up. For this table, percentages will be calculated using the number in patients in the safety population.

Additionally, the above table will summarize the number and percent of randomized patients in the following populations:

- Full Analysis set;
- Safety population;
- Per Protocol population;

8.3 Protocol deviations

Protocol deviations will be classified as minor or major and whether they led to exclusion of the patient from the Per Protocol Population prior to the database lock. Major protocol deviations overall and major protocol deviations leading to exclusion of the patient from the Per Protocol Population will be summarized by category and overall. All protocol deviations will be listed.

8.4 Demographics and baseline characteristics

Demographic and baseline patient characteristics will be summarized overall and by treatment group based on the safety population.

All demographic and other baseline characteristics will be provided in a listing.

8.4.1 Demographics

Following demographic characteristics will be summarized

- Age (years)at screening,
- Age category (<45, 45-64, 65-74, \geq 75 years, Not Reported)
- Gender (Male, Female)
- Ethnicity (Hispanic or Latino, Not Hispanic or Latino, Not reported)
- Race (American Indian or Alaska Native, Asian, Black or African American, Native Hawaiian or other Pacific Islander, White, Other, Not Reported)

Statistical Analysis Plan (SAP)

- Height (cm)
- Weight (kg) (for hemodialysis patients- prescription dry body weight)
- Body mass index (kg/m²)
- Female Reproductive status (Pre-menarche, Sterile, Post-menopausal, Potentially able to bear children, Other and Not applicable)

8.4.2 Baseline and disease characteristics

Baseline characteristics of the disease will also be summarized. Baseline disease characteristics include variables such as

- Glomerular filtration rate (GFR) (mL/min/1.73m²)
- Grouped GFR (<30 mL/min/1.73 m² or \geq 30 and <60 mL/min/1.73 m²)
- Renal disease status (Moderate CKD Non-Dialysis, Severe CKD Non-Dialysis, Severe CKD On Dialysis)
- Baseline NRS score

As a separate summary, the GFR (mL/min/1.73m²) and grouped GFR (<15 ml/min/1.73m², 15-29 ml/min/1.73m², 30-59 ml/min/1.73m², 60-89 ml/min/1.73m², >90 ml/min/1.73m²) will be summarized across patients who did not meet inclusion criteria #4 (renal status). If multiple GFR results were recorded during the screening/run-in period then the maximum will be used. This data will be listed in the screen failure listing (see [section 8.2](#)).

8.4.3 Medical History

Medical history data will be coded using Medical Dictionary for Regulatory Activities (MedDRA) version 21.0. A summary table by treatment group will be presented by MedDRA system organ class (SOC) and preferred term.

The data will also be listed including the verbatim Investigator description of the relevant medical condition, the coded terms (SOC, preferred term) start date, end date, and whether the condition is ongoing.

A separate coding listing will be created with all the distinct levels of SOC, High Level Terms, Preferred Terms, Lowest Level Term and the verbatim Investigator description reported in the study. Sorting will be alphabetically by SOC, Preferred Term, and then verbatim description.

8.4.4 Prior and concomitant medications

Prior medications (including vitamins and herbal supplements) are defined as those that the patient has taken any time during the 30 days prior to the screening up until the first dose of study drug on Day 1.

Concomitant medications are medications that the patient has taken after the start of the first dose of study drug on Day 1 of the Treatment period through the end-of-treatment (i.e., 12-week Treatment period)/early termination visit.

Statistical Analysis Plan (SAP)

All medications will be coded using the World Health Organization Drug Dictionary (WHODD) version March 2018. All prior and concomitant medications will be listed and summarized separately by Anatomical Therapeutic Chemical (ATC) class 3 and preferred term.

Additionally, a coding listing will be created which will include all distinct ATC class 1, 2 and 3 codes and preferred terms along with the corresponding verbatim description of the medications; sorting will be alphabetically by ATC class 3 and preferred term. Prior and concomitant medications will be listed separately.

8.4.5 Prior and concomitant procedures

Prior procedures are defined as those performed on the patient during the 30 days prior to the screening up until the first dose of study drug on Day 1.

Concomitant procedures are defined as those performed on the patient after the start of the first dose of study drug on Day 1 of the Treatment period through the end-of-treatment (i.e., 12-week Treatment period)/early termination visit.

All procedures will be coded using Medical Dictionary for Regulatory Activities (MedDRA) version 21.0. All prior and concomitant procedures will be listed and summarized separately by SOC and preferred term.

Additionally, a coding listing will be created which will include all distinct SOC, High Level Terms, preferred terms and Lowest Level Terms along with the corresponding verbatim description of the procedure; sorting will be alphabetically by SOC and preferred term. Prior and concomitant procedures will be listed separately.

